**CCI**

**CCI**

 GALDERMA	<small>Title</small> SAP, 43CH1626, Restylane Volyme Midface	<small>Doc id</small> MA-35135
--	--	--

CCI

## 2.5 Safety Analysis

All safety variables will be summarized descriptively based on the Safety population.

CCI

### 2.5.2 Adverse Events

All AEs will be coded according to MedDRA and summarized by System Organ Class (SOC) and Preferred Term (PT). All AE summaries defined below will be presented by treatment, i.e. no treatment at baseline vs. all treated subjects (at baseline and Month 6).

An overall summary of number and percentage of subjects with any AEs, including related/unrelated and serious AEs, and the number of events will be compiled (Table 10-5).

For related AEs, maximum intensity of the AE will be summarized (Table 10-6). The duration (Table 10-7) and time to onset (Table 10-8) of event will be summarized by SOC and PT using number of events, mean, standard deviation, minimum, median, and maximum statistics. Action taken due to a related AE will be summarized by SOC, and PT (Table 10-9) using number of events.

Number and percentage of subjects with unrelated AEs and number of events will be presented by SOC, PT and maximum intensity (Table 10-10).

Time to onset of an AE will be derived as the start date minus the date of the most recent treatment. If the start date is missing, it will be assumed that the AE started on the date of the most recent treatment.

Duration of an AE will be derived as the stop date minus the start date +1. If the start date is missing, it will be assumed that the AE started on the date of the most recent treatment. Missing stop date will not be imputed and therefore no duration will be calculated in these cases. Instead, the number of AEs that were ongoing at the end of the study will be given.

 GALDERMA	<small>Title</small> SAP, 43CH1626, Restylane Volyme Midface	<small>Doc id</small> MA-35135
---	--	--

[figure not shown]

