4.7 Schedule of events

Table 1. Schedule of Events for Group A and Treatment Group

	Group A and Treatment Group					
	Screening ^a	Baseline ^a / Initial treatment	Optional Touch-up ^b	Follow-up	Follow-up	Final visit / Early termination
	D-21 to D1	D1	4W($\pm 3d$) after randomization	4W($\pm 3d$) after Last treatment	3M($\pm 1w$), 6M($\pm 1w$) and 9M ($\pm 2w$) after last treatment	12M ($\pm 2w$) after last treatment
Informed consent	X					
Height, Demography	X					
Weight	X	X	X	X	X	X
Medical history & concurrent diseases	X	X				
Concomitant medication/procedures	X	X	X	X	X	X
Vital signs		X ^c				
Laboratory tests	X				X ^e	X ^f
ECG	X					
Pregnancy test		X ^c	X ^c			X
Inclusion and Exclusion criteria	X	X				
Randomization		X				
Treatment		X	X			
MMVS (Blinded Evaluator)	X	X ^c			X	X
CCI						
Photography		X ^c	X ^c	X ^d	X	X

CCI

Device deficiencies		X	X			
Assessment of AE	X	X	X	X	X	X
Study termination						X

- a) Screening visit and baseline visit can be combined to one visit if feasible.
- b) This visit is only for subjects who receive touch-up (If no touch-up performed, subjects will conduct the 4w after last treatment visit).
- c) Prior to treatment.
- d) Extra set of Photographs (taken 10 minutes after the first photos) will be taken and used for validation purpose as needed.
- e) Only performed at 6M.
- f) Only performed at early termination if termination occurs before 6 months visit after last treatment

Table 2. Schedule of Events for Control Group

Activity	Control Group									
	Screening ^a	Baseline ^a	Follow-up	Follow-up	Follow-up /Treatment	Optional Touch-up ^b	Follow-up	Follow-up	Final visit / Early termination	
	D-21 to 1	D1	4W(±3d) after randomization	3M (±1w) after randomization	6M(±1w) after randomization	4W(±3d) after 6M treatment	4W(±3d) after last treatment	3M (±1w) after last treatment	6M (±1w) after last treatment	
Informed consent	X									
Height, Demography	X									
Weight	X	X	X	X	X	X	X	X	X	
Medical history & concurrent diseases	X	X								
Concomitant medication/procedures	X	X	X	X	X	X	X	X	X	

Vital signs		X			X ^c					
Laboratory tests	X				X ^c					X
ECG	X									
Pregnancy test		X			X ^c	X ^c				X
Inclusion and Exclusion criteria	X	X								
Randomization		X								
Treatment					X	X				
MMVS (Blinded Evaluator)	X	X		X	X ^c			X		X
CCI										
Photography		X	X ^d	X	X ^c	X ^c	X	X		X
CCI										
Device deficiencies					X	X				
Assessment of AE	X	X	X	X	X	X	X	X		X
Study termination										X

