**CCI**

10.5 Safety Analysis

CCI

All AEs will be coded according to MedDRA.

 GALDERMA	Title 43CH1626 Clinical Study Protocol	Doc id MA-33281
--	--	---------------------------

Related AEs will be summarised by SOC, PT and intensity and by treatment. In addition, for related AEs the number of days to onset and the duration of event will be summarised by SOC and PT and treatment using mean, SD, min, max and median.

Serious AEs will be listed.

Non-related AEs will be summarised by SOC, PT, and intensity and by treatment.

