## 10.2 Adverse Events

### 10.2.1 Summary of Adverse Events (AEs)

**Table 10-5: Brief summary of all AEs, Safety population**

	Group A N = xx		Group B					
			No treatment at baseline N = xx		Treatment with Restylane Volyme N = xxx		Subjects	
	n	%	n	n	%	n	n	%
Any AEs reported, total								
AEs related to product and/or injection procedure								
Of which were serious								
AEs unrelated to product and/or injection procedure								
of which were serious								
Subjects with no AE reported								

% = n/N\*100

Note: Treatment with Restylane Volyme columns include data from subjects in the Restylane Volyme group after their initial treatment at baseline, as well as data from subjects in the Control group after their initial treatment at Month 6.

 GALDERMA	Title SAP, 43CH1626, Restylane Volyme Midface	Doc id MA-35135
---	---	---------------------------

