### 10.2.3 Unrelated AEs

**Table 10-10: Unrelated AEs by MedDRA System Organ Class, Preferred Term, and maximum intensity, Safety population**

Primary System Organ Class Preferred Term	Maximum intensity	No treatment at baseline N = xx		Treatment with Restylane Volyme N = xxx		Total N = xx	
		Subjects	Events	Subjects	Events	Subjects	Events
		n (%)	n	n (%)	n	n (%)	n
Any related AE	Total						
	Mild						
	Moderate						
	Severe						
SOC1	Total						
	Mild						
	Moderate						
	Severe						
PT11	Total						
	Mild						
	Moderate						
	Severe						
PT12	Total						
	Mild						
	Moderate						
	Severe						
SOC2	Total						
	Mild						
	Moderate						
	Severe						
PT21	Total						
	Mild						
	Moderate						
	Severe						

% = n/N\*100

Note: Treatment with Restylane Volyme columns include data from subjects in the Restylane Volyme group after their initial treatment at baseline, as well as data from subjects in the Control group after their initial treatment at Month 6.

 GALDERMA	<small>Title</small> SAP, 43CH1626, Restylane Volyme Midface	<small>Doc id</small> MA-35135
--	--	--

2017-11-03 11:43

Effective date:

*Effective*

Version: 1.0

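### The adverse event tables set about 6 months of untreated observation beside a pooled treated column averaging 10.5 to 11.4 months, and no visible AE table compares the randomised arms over one window

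*SAP*

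**What the plan says.** SAP section 2.5.2 gives one column rule for all AE summaries: "no treatment at baseline vs. all treated subjects (at baseline and Month 6". The notes under the tables define the second column. Under Table 10-5: "Treatment with Restylane Volyme columns include data from subjects in the Restylane Volyme group after their initial treatment at baseline". The same notes, for example under Table 10-10, add "data from subjects in the Control group after their initial treatment at Month 6". A control who accepts treatment therefore contributes to both columns.

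Tables 10-5 and 10-10 report subjects (n and n/N as a percentage) and event counts. Neither shows subject-time or a common cut-off. Table 10-5 carries the any-AE, related and unrelated rows, with serious events nested under the last two. Table 10-10 covers unrelated AEs by SOC, PT and intensity.

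The protocol points the same way. Section 10.5 states "Non-related AEs will be summarised by SOC, PT, and intensity and by treatment", and separately "Serious AEs will be listed". In both documents the Safety population is analysed as treated. SAP section 2.5 makes all safety summaries descriptive.

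**The concern.** AE incidence is a stated safety endpoint, and a no-treatment control can show how many AEs would occur anyway. A crude percentage rises with the length of observation. If one column is observed nearly twice as long as the other, its percentage of subjects with an unrelated AE will be higher even when the product has no effect on such events. A reader of the study report could take that difference for a treatment effect, or dismiss a real one as follow-up time. The randomised comparison over equal time would settle which, but no visible AE table gives it. Table 6-2 is by randomised arm, but it counts medications over the whole study, by which time controls may have been treated.

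**Working it through.** **Inputs from the documents.** Group B has 111 Treatment Group and 37 Control Group subjects (Protocol synopsis). Treatment Group follow-up ends 12 months after last treatment; controls are offered treatment at Month 6 and followed to 6 months after last treatment (Protocol Tables 1 and 2). The optional touch-up comes 4 weeks after initial treatment, so t = 0 or 28/30.44 = 0.92 months. Screening takes up to 21 days, or 0.69 months.

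**Check against the stated duration.** Treatment Group: 0.69 + 0.92 + 12 = 13.6 months. Control Group: 0.69 + 6 + 0.92 + 6 = 13.6 months. Both fit the protocol's figure of about 14 months.

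**Mean time in the treated column**, if all controls accept treatment and nobody withdraws:
- no touch-up: (111 × 12 + 37 × 6)/148 = 1554/148 = 10.5 months;
- all touched up: (111 × 12.92 + 37 × 6.92)/148 = 11.4 months.

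Against 6 untreated months, the ratio of observation time is 1.75 to 1.90.

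**Effect on unrelated-AE percentages.** The documents give no background rate, so the untreated 6-month incidence p is assumed over a range, with the same constant hazard in both columns:
- h = -ln(1 - p)/6
- treated = [111 × (1 - exp(-h(12 + t))) + 37 × (1 - exp(-h(6 + t)))]/148

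Example at p = 20%, t = 0: over 12 months the incidence is 1 - 0.8² = 36%, so treated = 0.75 × 36% + 0.25 × 20% = 32.0%.

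| Untreated | Treated, no touch-up to all touched up | Ratio |
|---|---|---|
| 5% | 8.6-9.3% | 1.71-1.86 |
| 10% | 16.8-18.1% | 1.68-1.81 |
| 20% | 32.0-34.3% | 1.60-1.71 |
| 30% | 45.8-48.6% | 1.53-1.62 |

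**Any-AE row.** Protocol section 8.4.8 expects injection reactions to begin on the day of treatment and typically to resolve within a week. Subjects who have one are already counted, so longer observation adds less. If a fraction r of treated subjects has an early related AE, independent of background events, the excess due to longer observation is (1 - r) × (treated - p). At p = 20% the 12.0-14.3 points become 8.4-10.0 at r = 30%, 6.0-7.1 at r = 50% and 3.6-4.3 at r = 70%. These r values are assumptions.

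**What moves the ratio.** AEs are collected from consent. If screening AEs entered the untreated column for the full 21 days, the ratio at p = 10% would fall from 1.68-1.81 to 1.51-1.63. That is a maximum, because "Screening visit and baseline visit can be combined to one visit if feasible". Controls who decline treatment move it either way. If 20% declined (an assumption), the ratio at 10% would be 1.45-1.56 if their later time counted as untreated, and 1.71-1.84 if it entered no column.

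**Precision of a fair comparison.** The 95% CI half-width is 1.96 × sqrt(p(1 - p)(1/111 + 1/37)): 14.9 points at p = 20% in both arms and 8.1 at 5%.

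**The case against.** The planned layout follows the plan's own definitions. The AE endpoint covers the whole study, the protocol asks for summaries by treatment, and the Safety population is as treated. Pooling everyone who received the product is a reasonable description of exposure. The summaries are descriptive, with no AE hypothesis test in the visible text, and the table notes disclose the pooling. Unequal follow-up can be read from SAP Tables 4-5 and 4-6. Related AEs, the main device signal, have their own time-to-onset and duration tables. A same-window table is therefore an addition and does not repair a contradiction. It would also be imprecise: its 14.9-point half-width at 20% exceeds the 12.0-14.3-point artefact that it removes.

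All of that stands, and it limits the weight of the point. It does not make the two printed percentages comparable. Imprecision is shown by an interval; an unequal window is not.

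A reader might go further and infer that the plan inflates or hides harm. The documents do not support that: the longer window raises the treated percentage, which works against the product, and the pooling is stated openly. Nor should the table of percentages above be applied to every AE row. It assumes a constant background hazard and no early injection reactions, which suits only the unrelated rows.

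A reader might also call the placement of screening AEs, and of later AEs in controls who decline treatment, a gap in the plan. The notes keep both out of the treated column, and the visible text does not say where they go. SAP section 2.1 is redacted and may contain the rule, so a gap cannot be asserted.

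**Conclusion.** The point holds as a limit on interpretation. Tables 10-5 and 10-10 compare about 6 months with a mean of 10.5-11.4 months, and under equal constant hazard the unrelated-AE percentage would appear about 1.5 to 1.9 times as high under treatment for untreated incidences of 5% to 30%. This rests on an assumed background rate, full acceptance of the Month 6 treatment, no withdrawal, and an untreated column ending at Month 6. The any-AE excess is smaller by the factor (1 - r). Related AEs are little affected, because untreated subjects should have almost none. Serious AEs are to be listed individually and have no rows of their own in Table 10-10. No formal test or primary conclusion depends on this, and the change is optional.

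**What to change.** Keep the pooled treated column as an exposure summary. Add to SAP section 2.5.2 one descriptive Group B table in the Safety population: any, related and unrelated AEs, with serious events nested as in Table 10-5, giving n, percentage and events. Show it by randomised arm; any subject treated contrary to allocation is shown as treated and footnoted, which keeps the table consistent with the as-treated population.

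Count AEs with onset from randomisation to 6 calendar months after randomisation in both arms, ending before the Month 6 injection in controls. Do not reuse the effectiveness definition of Month 6, which runs from last treatment in the Treatment Group. A touched-up subject would then have 6.92 months against 6, and (1 - exp(-6.92h))/p leaves a ratio of 1.14 at p = 10% and 1.12 at 30%.

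Optionally, add subject-months and exposure-adjusted rates to the unrelated row of Table 10-5 and to Table 10-10 only. In the other rows they would dilute front-loaded reactions: one first-week event in 10% of subjects is 10/6 = 1.7 per 100 subject-months over 6 months, but 10/11.4 to 10/10.5 = 0.9-1.0 over the treated column's follow-up.

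If no rule in SAP section 2.1 already covers it, state where screening AEs and decliners' later AEs are counted. As a separate clerical correction that lends this point no support, relabel the top row of Table 10-10, printed "Any related AE" in a table titled "Unrelated AEs by MedDRA System Organ Class, Preferred Term, and maximum intensity, Safety population".

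The cost is a little programming, since AE, randomisation and treatment dates are already collected. The added table will show only a large excess, and AE reporting and causality assessment remain open-label.

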Effectiveness Assessment:	
Medicis Midface Volume Scale (MMVS):
 
MMVS is a Four-Point scale that assesses the fullness of the midface from Fairly Full (1) to Substantial Loss of Fullness (4) as described below. The blinded evaluator and CCI [REDACTED] will rate the subject's right and left midface for severity of volume deficiency using the MMVS at all applicable study visits.
 
CCI
	

 GALDERMA	Title 43CH1626 Clinical Study Protocol	Doc id MA-33281
---	--	---------------------------

Effective date: 2016-12-09 17:18

Effective

Version: 1.0

	CCI
	CCI
Safety Assessment:	AE will begin to be collected after ICF signed. Each subject will be questioned about AEs at each clinical visit following the screening visit. The question asked will be “Since your last clinical visit have you had any health problems?” Information on AEs can also be obtained from laboratory test report, signs and symptoms detected during each examination, observations by the study

	Title 43CH1626 Clinical Study Protocol	Doc id MA-33281
--	--	---------------------------

Effective date: 2016-12-09 17:18

Effective

Version: 1.0

	
personnel, subject diaries or spontaneous reports from the subjects.
 
CCl

Statistical Methods:	
All summaries will be done separately for Group A and B. CCl
 
Primary analysis
 
The percentage of responders (a responder will be defined as a subject with at least 1 point improvement from baseline MMVS on both sides of the face concurrently) will be calculated for Treatment Group at 6 months after last treatment, and for Control Group at 6 months after randomization based on the blinded evaluator's assessment. CCl
 
CCl

	
CCl

	
Safety
 
CCl
 
Adverse event incidences will be summarized by MedDRA system organ class (SOC) and preferred term (PT).
 
Sample size

 GALDERMA	<small>Title</small> 43CH1626 Clinical Study Protocol	<small>Doc id</small> MA-33281
---	---	--

Effective date: 2016-12-09 17:18

Effective date:

Effective

Version: 1.0

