3.2 Endpoints of the study

3.2.1 Primary effectiveness endpoint:

- Percentage of responders, defined by at least 1 point improvement from baseline on the MMVS on both sides of the face concurrently, as measured by blinded evaluator at 6 months after last treatment in Treatment Group, and at 6 months after randomization in Control Group.

CCI

 GALDERMA	<small>Title</small> 43CH1626 Clinical Study Protocol	<small>Doc id</small> MA-33281
--	---	--

CCI

3.2.3 Safety endpoints:

- Incidence, intensity, duration, and onset of adverse events (AEs) collected throughout the study.

CCI

4 Design of the Study

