4.4.2 Blinding

Only the evaluator will be blinded, both treating investigator and subjects will be open-labelled.

The Blinded Evaluator shall not be allowed to retrieve study supplies or to be present during opening of the study supplies or injections. The Treating Investigator is not allowed to discuss treatments with the blinded evaluator or the subjects. All documents with information on study products shall be kept in a separate binder not available to the blinded evaluator.

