## 1.5 Safety Assessments

CCI

A two-point scale ('Yes' or 'No') will be used to assess causality of AEs, serious as well as non-serious. The Investigator shall be asked to indicate a response to each of the following questions in the electronic case report form (eCRF):

- *"Do you consider that there is a reasonable possibility that the event may have been caused by the study product?"* and
- *"Do you consider that there is a reasonable possibility that the event may have been caused by the study product injection procedure?"*

If any of these questions are answered with a 'Yes', the AE will be considered related.

 GALDERMA	<small>Title</small> SAP, 43CH1626, Restylane Volyme Midface	<small>Doc id</small> MA-35135
--	--	--

[figure not shown]
Each AE will also be assessed for causal relationship and seriousness by the Sponsor, in order to fulfill regulatory requirements. In case of a disagreement, the AE will be considered '*Related*'.

Any device deficiencies discovered in relation to treatment at baseline and 4-week follow-up visits for the Treatment Group and treatment at 6 months after randomization and 4-week follow-up after 6-moth treatment for the Control Group will be recorded.

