### 10.2.2 Related AEs

**Table 10-6: Related AEs occurring throughout the whole study period by MedDRA System Organ Class, Preferred Term, and maximum intensity, Safety population, Group B**

Primary System Organ Class Preferred Term	Maximum intensity	No treatment at baseline N = xx		Treatment with Restylane Volyme N = xxx		Total N = xx	
		Subjects	Events	Subjects	Events	Subjects	Events
		n (%)	n	n (%)	n	n (%)	n
Any related AE	Total						
	Mild						
	Moderate						
	Severe						
SOC1	Total						
	Mild						
	Moderate						
	Severe						
PT11	Total						
	Mild						
	Moderate						
	Severe						
PT12	Total						
	Mild						
	Moderate						
	Severe						
SOC2	Total						
	Mild						
	Moderate						
	Severe						
PT21	Total						
	Mild						
	Moderate						
	Severe						

% = n/N\*100

Note: Treatment with Restylane Volyme columns include data from subjects in the Restylane Volyme group after their initial treatment at baseline, as well as data from subjects in the Control group after their initial treatment at Month 6.

 GALDERMA	Title SAP, 43CH1626, Restylane Volyme Midface	Doc id MA-35135
---	---	---------------------------

**Table 10-7: Duration (number of days days) of related AEs occurred throughout the whole study period by MedDRA System Organ Class and Preferred Term, Safety population, Group B**

Primary System Organ Class Preferred Term	No treatment at baseline N = xx					Treatment with Restylane Volyme N = xxx					Total N = xxx				
	N (events)	Duration missing	Mean (SD)	Median	Min-Max	N (events)	Duration missing	Mean (SD)	Median	Min-Max	N (events)	Duration missing	Mean (SD)	Median	Min-Max
SOC1															
PT11															
PT12															
Total															

Note: Treatment with Restylane Volyme columns include data from subjects in the Restylane Volyme group after their initial treatment at baseline, as well as data from subjects in the Control group after their initial treatment at Month 6.

**Table 10-8: Time to onset (days) since most recent treatment of related AEs by MedDRA System Organ Class and Preferred Term, Safety population, Group B**

Primary System Organ Class Preferred Term	No treatment at baseline N = xx				Treatment with Restylane Volyme N = xxx				Total N = xxx			
	N (events)	Mean (SD)	Median	Min-Max	N (events)	Mean (SD)	Median	Min-Max	N (events)	Mean (SD)	Median	Min-Max
SOC1												
PT11												
PT12												
Total												

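### No visible adverse event table gives all-cause incidence by system organ class and preferred term, although the SAP and protocol synopsis promise it and the safety endpoint requires it

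*SAP*

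**What the plan says.** The general undertakings carry no causality restriction. SAP 2.5.2 opens with "All AEs will be coded according to MedDRA and summarized by System Organ Class (SOC) and Preferred Term (PT"), and the statistical methods part of the protocol synopsis has "Adverse event incidences will be summarized by MedDRA system organ class (SOC) and preferred term (PT"). The safety endpoint in Protocol 3.2.3, repeated in SAP 1.6, is "Incidence, intensity, duration, and onset of adverse events (AEs) collected throughout the study".

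SAP 2.5.2 then assigns table numbers, and the causality split begins there. Table 10-5 is an overall count. Table 10-6 is titled "Related AEs occurring throughout the whole study period by MedDRA System Organ Class, Preferred Term, and maximum intensity", and Tables 10-7 to 10-9 give duration, onset and action taken, again for related events. The last entry is "Number and percentage of subjects with unrelated AEs and number of events will be presented by SOC, PT and maximum intensity (Table 10-10"). The readable part of Protocol 10.5 divides events in the same way: related events first, then "Non-related AEs will be summarised by SOC, PT, and intensity and by treatment".

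SAP 2.5.2 says that every AE summary sets subjects untreated at baseline against all treated subjects. The treated column includes controls after their Month 6 injection.

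On causality, Protocol 8.4.3.2 and SAP 1.5 ask the investigator two yes/no questions, one about the product and one about its injection. A single yes makes the event related. On blinding, Protocol 4.4.2 says "Only the evaluator will be blinded, both treating investigator and subjects will be open-labelled". The sponsor makes a second assessment; on that, SAP 1.5 says "In case of a disagreement, the AE will be considered" related.

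**The concern.** A reader who wants to know how many treated and untreated subjects had, say, headache will find no table that answers directly. Each term-level display is first filtered by a judgement that depends on whether the subject has been injected. Someone not yet injected has essentially no route to a yes on either causality question, so Table 10-6 compares the treated column with a near-structural zero. Table 10-8 shows the difficulty plainly: onset is counted from the most recent treatment, which untreated subjects do not have.

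Table 10-10 has the opposite problem. A background event called related in a treated subject moves out of it, while the same event in an untreated subject stays. The sponsor's review can only enlarge the related set, because either party's yes is enough.

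At stake is the term-level description of safety in a study that Protocol 2.5 says will support registration. A non-specific event could be divided between two tables, with neither showing its full frequency in treated subjects. This would remain even if follow-up were equal in the two columns.

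**Working it through.** **Step 1. Inventory of the visible AE tables (SAP 2.5.2 and Appendix 10.2).**

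| Table | SOC/PT rows | Events included |
|---|---|---|
| 10-5 | No | All, with related/unrelated and serious sub-counts |
| 10-6 | Yes | Related only (maximum intensity) |
| 10-7 | Yes | Related only (duration) |
| 10-8 | Yes | Related only (onset) |
| 10-9 | Yes | Related only (action taken) |
| 10-10 | Yes | Unrelated only (maximum intensity) |

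Five tables have SOC/PT rows: four related only, one unrelated only, none all-cause. The SAP contents list agrees: section 10.2 consists of a summary, related AEs and unrelated AEs.

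**Step 2. What can be rebuilt.** For one term and one column, let r be the subjects in Table 10-6, u the subjects in Table 10-10 and N the denominator.

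- Events: all-cause = related + unrelated, exactly.
- Subjects: all-cause lies between max(r, u) and min(N, r + u), because a subject with both a related and an unrelated event of that term is counted in each table.

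The synopsis plans 111 treated and 37 control subjects. If every control accepts treatment at Month 6, the treated column has N = 111 + 37 = 148; if none does, N = 111. The counts below are assumed for illustration.

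| r | u | All-cause subjects | % of 148 | % of 111 |
|---|---|---|---|---|
| 12 | 0 | 12 | 8.1 | 10.8 |
| 12 | 3 | 12 to 15 | 8.1 to 10.1 | 10.8 to 13.5 |
| 12 | 6 | 12 to 18 | 8.1 to 12.2 | 10.8 to 16.2 |
| 6 | 6 | 6 to 12 | 4.1 to 8.1 | 5.4 to 10.8 |

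The result is exact when r or u is zero, or when no subject has both kinds of event for that term. In the untreated column r is essentially zero, so Table 10-10 there already gives nearly the all-cause figure. The uncertainty falls on the treated column.

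**Step 3. Direction of the shift in Table 10-10.** Suppose equal follow-up, no true effect on the term, background incidence b in both columns, and a fraction a of affected treated subjects whose events are all called related. The expected unrelated percentage is b(1 − a) in treated subjects and b in untreated subjects. With b = 20% (assumed):

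| a (assumed) | Treated, unrelated | Untreated, unrelated |
|---|---|---|
| 0% | 20% | 20% |
| 10% | 18% | 20% |
| 30% | 14% | 20% |
| 50% | 10% | 20% |

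The direction is fixed for any a above zero. The size is not, since the documents give neither a nor b.

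**The case against.** The strongest reply is that the all-cause summary is already planned in words, so only a table shell is missing. The shells do not look exhaustive either. Protocol 10.5 says serious events will be listed, yet no shell for this is visible, and SAP section 6.2 carries a note to consider another table. This is fair, and it is why the point concerns undelivered text rather than a decision to omit all-cause incidence. It does not remove the point, because a programmer following the numbered summaries would produce only the split tables.

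Three stronger readings are tempting, and the documents do not support them.

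- *Term-level incidence cannot be recovered.* Event counts add exactly and subject counts are bounded. Protocol 8.4.8 anticipates mainly injection-site reactions, for which one table may hold nearly all subjects and the bounds will be narrow.
- *The plan would usually show a spurious deficit of unrelated events in treated subjects.* This depends on the assumed attribution rate. With 111 v 37 subjects and 20% background incidence, the treated percentage falls below the untreated one in about 47% of simulated trials with no reattribution at all, and in about 57% when 10% of events are called related. No frequency can be claimed without knowing the rate.
- *No AE table anywhere is all-cause.* Table 10-5 is, overall. Safety material before Appendix 10.2 and the start of Protocol 10.5 are blacked out and are not judged here.

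It also stands that SAP 2.5 keeps safety descriptive, that counting disagreements as related is cautious for a device's own safety profile, and that open-label reporting would affect an all-cause table too. A displayed empty column is a layout matter and need not be removed.

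**Conclusion.** The point holds in limited form. Two general statements and the endpoint call for AE incidence by term regardless of cause, and none of the visible summaries in Tables 10-5 to 10-10 or Protocol 10.5 provides it. Every term-level treated v untreated display is conditioned on an unblinded judgement that can hardly be yes before injection. As a result, the number and percentage of treated subjects per term may be known only as a range, and Table 10-10 can shift in one direction by an unknown amount.

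This rests on the readable text and on the assumption that the blinded evaluator does not judge causality; no passage gives the evaluator that task. The illustrative counts and rates are assumptions. The primary effectiveness analysis is unaffected. The change should be made because it costs little and delivers what the plan already says, not because a particular distortion has been shown.

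**What to change.** 1. Add one table to SAP Appendix 10.2: all AEs regardless of causality, by SOC, PT and maximum intensity, with each subject counted once per term, event counts alongside, and the same treatment columns as the existing tables.
2. In SAP 2.5.2, cite that table beside the opening sentence and state that any treated v untreated description of AEs uses it, with Tables 10-6 and 10-10 supportive.
3. In the same place, note the different follow-up lengths. Under the protocol's schedules of events, the untreated column covers about 6 months. The treated column covers up to 12 months after last treatment in the Treatment Group and 6 months after last treatment in controls. The new table does not correct for this.
4. Align Protocol 10.5 with a matching line.

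The cost is one table, a few sentences in the SAP and one line in the protocol. The data are already collected under Protocol 8.4.3, and study conduct does not change.
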